**Chief investigator contacts details**

[name]  
 Clinical Psychology Unit, [name]  
 Email: [contact]

Contents of the study protocol	Pg.
1. Synopsis	2
2. Background and rationale	3
3. Objectives and research questions	3
4. Study design	4
4.1 Setting and participants	4
4.2 Intervention	5
4.3 Measures	5
4.4 Recruitment, study procedures and data collection	6
5. Data analysis	6
6. Ethical considerations	7
7. Dissemination plan	
8. References	8

1. Synopsis of the study	
Short study title	CPM Trial
ISRCTN registration no.	TBC
Study Design	Pragmatic, stepped-wedge randomised controlled trial
Setting	Adult Community Nursing services across the geography of Rotherham Doncaster and South Humber NHS Foundation Trust
Study Participants	Registered nurses that work in the National Health Service
Primary Objective	To evaluate if a group-based psychological intervention reduces occupational burnout levels in a cohort of nurses
Secondary Objectives	
 
▪ To assess if the intervention improves subjective well-being
 
▪ To assess if the intervention reduces self-reported sickness absence
 
▪ To quantify completion and dropout rates
 

Primary outcome	Occupational burnout, measured by the Oldenburg Burnout Inventory (OLBI)
Intervention	An 8-week, group-based, psychoeducational intervention based on The Chimp Paradox Model
Randomization and data collection	Consenting NHS staff will be randomly assigned to two groups; 1 and 2. Participants in both groups will be asked to complete outcome measures at an initial baseline assessment, after which only participants in group 1 will access an 8-week intervention ( controlled phase ). Next, group 2 will access the intervention during an 8-week period ( full implementation phase ). Finally, we will collect further outcome measures 6 months after both groups have completed the intervention ( follow-up phase ).
Planned Sample Size	Minimum recruitment target of 192 participants, expecting 30% attrition.
Data analysis method	
 
1. Trial data will be summarised using a CONSORT diagram and analyses will be based on intention-to-treat principles.
 
2. Between-group comparisons will be conducted at the end of each phase using ANOVA.
 
3. The primary analyses will examine between-group differences in occupational burnout (OLBI) severity over time (after each of the 3 phases, post-baseline).
 
4. Secondary analyses will involve comparing between-group differences in each of the OLBI burnout dimensions (exhaustion, disengagement), and in measures of subjective well-being and personal goal attainment.
 
5. We will also quantify and report intervention completion / dropout rates, and self-reported days on sickness leave.
 

Study Period	24 months (18 months active study period, plus 6 months analyses and dissemination)

## 2. Background and rationale

Occupational burnout refers to a state of job-related emotional exhaustion, depersonalisation and reduced personal accomplishment (Maslach, 1982). Burnout is known to be particularly acute in healthcare professionals, and especially in mental health workers, affecting around 40% according to a recent meta-analysis (O'Connor, Muller, Neff, & Pitman, 2018). Previous studies have demonstrated that burnout has a negative impact on psychological well-being and physical health (Salvagioni et al., 2017). Burnout is also associated with poorer job performance (Taris, 2006), and increased absenteeism and staff turnover (Lee, Lim, Yang, & Lee, 2011; Salvagioni et al., 2017). Furthermore, increased burnout not only has adverse consequences for healthcare professionals, but is also associated with poorer patient treatment outcomes (Delgadillo, Saxon, & Barkham, 2018), medical errors (Shanafelt et al., 2010), medico-legal cases (Balch et al., 2011), and healthcare related infections (Cimiotti et al., 2012).

A recent examination of staff well-being in the English National Health Service concluded that staff shortages associated with occupational stress are associated with poor quality of care and poor patient experience (Sizmur & Raleigh, 2018), highlighting the widespread nature of burnout and its impact in the NHS. Burnout in the National Health Service (NHS) is a system wide problem with Public Health England estimating the cost of staff absence due to poor health at £2.4 billion per annum. The NHS depends on having a healthy and productive workforce to deliver high quality patient care. The Boorman NHS Health and Well-being 2009 report found that 80% of staff felt that their health and wellbeing had an impact on patient care, but only 40% of staff felt their employer was proactively trying to improve their health and wellbeing. The importance and impact of these issues has led experts, including The Royal College of Physicians (RCP), to call for NHS organisations to prioritise the health, wellbeing and engagement of staff. Their 2015 report '*Work and wellbeing in the NHS: why staff health matters to patient care*' outlines the fundamental importance of staff health and wellbeing to both NHS organisation and patients and concludes that our healthcare system's greatest asset is the people who deliver it. As NHS services face unprecedented clinical demand, increasing financial pressures and a patient population with complex care needs, it is often the health and wellbeing of NHS staff that suffers. For these reasons, and given the scale of the problem, the NHS Long Term Plan acknowledges the need to "support improved health and wellbeing of staff and management of sickness absence" (NHS England, 2019, pg. 87).

Approaches to address occupational burnout include individual interventions (e.g., stress management courses, mindfulness courses, cognitive-behavioural coping skills training, communication training) and structural / organisational interventions (e.g., workload redesign, practice delivery changes). Numerous studies have assessed the remedial or preventive effect of such interventions, although relatively few controlled trials have been conducted with healthcare professionals. A meta-analysis of controlled trials and cohort studies concluded that both individual-focused and organisational strategies can reduce burnout in physicians by approximately 10% (West, Dyrbye, Erwin, & Shanafelt, 2016). Although cohort studies generally indicate beneficial effects of these interventions, the more stringent pooled effect size from randomised controlled trials in this meta-analysis was not statistically significant. Another meta-analysis of randomised controlled trials found that cognitive-behavioural coping skills significantly reduced overall burnout in nurses, with maintenance of effects up to 1-year follow-up (Lee, Kuo, Chien, & Wang, 2016). The literature of controlled investigations of burnout remediation interventions for mental health workers is smaller, with mixed results, and inconclusive according to a systematic review which lacks a quantitative meta-analysis (Morse, Salyers, Rollins, Monroe-DeVita, & Pfahler, 2012). Overall, there is some evidence that individual and organisational interventions can help to alleviate occupational burnout, and coping-skills interventions appear to be particularly promising in healthcare staff. In spite of this emerging literature, evidence-based interventions to prevent or remediate burnout are not commonly or routinely available to NHS staff.

*The Chimp Paradox* model (CPM) is a mind management approach created by [name], a Consultant Psychiatrist (Peters, 2012). The model is based on developments in neuroscience. It

offers practical strategies and skills for the individual to learn how to: (1) gain insight into how their mind is working; (2) understand and recognise their thoughts, behaviours and emotions; (3) better manage themselves to become the person they would like to be. The model has been implemented in the world of elite sport, with public sector organisations, in the entertainment sector, in the corporate sector and with individuals over the past two decades. The CPM was first published in 2010 and has now sold over 1 million copies worldwide and was ranked The Sunday Times Number 1 Business Book from 2014 to 2017. A number of (unpublished) small pilot studies have been conducted using the model with groups of NHS staff, both in primary and secondary care. These pilot programmes have shown preliminary indications that the CPM could lead to improvements in the quality of life and wellbeing of the NHS staff in both their personal and professional lives. However, to date, rigorous and experimental support for this model is lacking. The CPM was developed in order to help individuals understand themselves better and help them to achieve personal success. We aim to assess whether system-wide implementation of the model amongst a cohort of NHS staff, and the collective impact on individuals, could translate to reduced burnout, improve wellbeing and reduce sickness absence.

This study aims to assess if access to a group-based intervention based on the CPM may lead to changes in occupational burnout and well-being in healthcare professionals. This will be the first experimental test of this intervention in the NHS.

### 3. Objectives and Hypotheses

#### 3.1. Primary Objective

To evaluate if a group-based psychological intervention reduces occupational burnout levels in healthcare professionals.

#### 3.2. Secondary Objectives

- To assess if the intervention improves subjective well-being
- To assess if the intervention improves personal goal attainment
- To assess if the intervention reduces sickness absence
- To quantify completion and dropout rates

[figure not shown]
#### 3.3. Hypotheses

- A) Exposure to the intervention will be associated with significantly lower mean burnout severity by comparison to a waitlist (delayed intervention) control group
- B) After the control group is exposed to the intervention, there will be no significant differences in mean burnout level between the two groups (immediate intervention group, delayed intervention group)
- C) Mean burnout severity for all participants at the end of the 6-month follow-up period will be significantly lower than baseline severity (prior to intervention), but not significantly different to end-of-treatment severity, indicating maintenance of gains

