### 4. Study design

This will be a pragmatic, stepped wedge, open-label, randomised controlled trial. Consenting NHS staff will be randomly assigned to two groups, by a research assistant using a computerized randomization algorithm (applying a simple 1:1 randomization schedule). The study will be carried out in four phases, which are illustrated in Figure 1.

Figure 1. Stepped wedge trial design

Participants in both groups will be asked to complete outcome measures during a pre-intervention baseline assessment (week 0). After the baseline assessment, only participants in group 1 will access an 8-week intervention (controlled phase). Next, group 2 will access the intervention during an 8-week period (full implementation phase). Finally, we will collect further outcome measures 6 months after both groups have completed the intervention (follow-up phase). The outcome measures will be completed continuously at each of the measurement points outlined in the above timeline (weeks 0, 8, 16, 40). All measures will be completed online using an industry-standard survey system (Qualtrics – which automatically sends email reminders to consenting participants), which will be managed by a research assistant.

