## 5. Data analysis

### 5.1. Sample size calculation

A sample size calculation was performed using the method described by Cohen (1992). There is no precedent for this type of trial in this setting, so it is not known whether exposure to the CPM intervention may be associated with small, moderate or large effects on measures of occupational burnout or well-being. We have therefore followed conventional sample size calculation methods described by Cohen (1992), expecting a moderate effect size as a conservative assumption. In order to detect a moderate effect size using between-groups ANCOVA, with 80% power, and an alpha level of 0.05, and controlling for intake severity, we estimate that at least 67 participants are needed per group. This would yield a minimum sample size of 134. Expecting a 30% dropout rate, which is common in studies of psychological interventions, we would need to inflate the recruitment target to 192.

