### 5.3. Secondary analyses

ANCOVA (and sensitivity analyses) described above will be repeated at each of the time-points illustrated in Figure 1 (weeks 0, 8, 16, 40), using the OLBI (total score; then separate domain scores), and using the WEMWBS as an outcome, controlling for baseline scores. Outcomes at 6-months follow-up (pooled for both groups) will be compared to outcomes at the baseline assessment, using paired-samples t-tests (or an appropriate non-parametric test depending on the distribution of the data).

We will carry out an exploratory analysis of sickness absence, by comparing the mean number of sickness absence days reported by all participants for the 6 months preceding the start of the study, and the mean sickness absence days reported during the 6-month follow-up period after both groups completed the intervention. This within-group comparison will be carried out using a paired-samples t-test (or an appropriate non-parametric test depending on the distribution of the data).

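### Hypothesis C reads a non-significant difference from end of treatment as maintenance, with no margin and no stated test; hypothesis B uses the same criterion

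*Protocol*

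**What the plan says.** Protocol section 3.3 states three hypotheses. A is the superiority comparison at week 8. B says that once the delayed group has been treated "there will be no significant differences in mean burnout level between the two groups". C has two halves that must both hold: burnout at the end of follow-up is significantly below baseline, "but not significantly different to end-of-treatment severity, indicating maintenance of gains". Neither B nor C names a margin.

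Section 5.3 repeats the between-group ANCOVA at the later assessments, which provides a test for B. For change over time in burnout and well-being it says: "Outcomes at 6-months follow-up (pooled for both groups) will be compared to outcomes at the baseline assessment, using paired-samples t-tests". The synopsis lists only between-group comparisons for these outcomes. No comparison of follow-up with end of treatment appears in the protocol.

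Section 5.1 sizes the trial to find a difference, not to exclude one: "In order to detect a moderate effect size using between-groups ANCOVA, with 80% power". It arrives at 67 per group, 134 in total, and 192 recruited to allow for 30% dropout.

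**The concern.** A non-significant test shows that the data did not rule out zero. It does not show that the difference is small. To conclude that gains were maintained, one needs a limit on how much loss would still count as maintenance, and a confidence interval that excludes anything larger. Hypothesis C has neither, yet it states the conclusion outright.

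C has a second gap. Its maintenance half has no analysis in section 5.3, so an analyst following the protocol would have to invent the contrast and decide what end of treatment means. The groups are treated one after the other, so end of treatment is week 8 for Group 1 and week 16 for Group 2.

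At stake is whether the report claims durable benefit, or agreement between the groups after both are treated, on data that would also be compatible with a real loss or a real remaining gap.

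**Working it through.** **Inputs from the protocol.** 67 per group, 134 analysed, 192 recruited, alpha 0.05, 80% power (section 5.1); assessments at weeks 0, 8, 16 and 40 (section 4); imputation by expectation-maximization before analysis (section 5.2), so that up to 96 per group may be analysed.

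**Assumptions.** Two-sided testing; differences in SD units; a moderate effect taken as d = 0.5; correlation r between repeated OLBI scores, shown as a range. The protocol gives none of these.

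**The plan's own figure.** An exact two-sample t calculation at d = 0.5, and an ANCOVA with f = 0.25 and one covariate, both give 64 per group. The stated 67 is slightly larger and gives power 0.82. The dropout step reproduces: 134 / 0.70 = 191.4, rounded up to 192. The small gap between 64 and 67 is on the safe side and has no bearing here.

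**Hypothesis B: chance of a non-significant week-16 result when a 0.3 SD gap is real.** SE = sqrt(2/n) × sqrt(1 − r²); the probability comes from the noncentral t distribution with noncentrality 0.3/SE.

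| n per group | r | SE | 95% CI half-width (1.96 × SE) | Non-significant |
|---|---|---|---|---|
| 67 | 0 | 0.173 | 0.34 | 59% |
| 67 | 0.6 | 0.138 | 0.27 | 42% |
| 96 | 0 | 0.144 | 0.28 | 46% |
| 96 | 0.6 | 0.115 | 0.23 | 27% |

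At a gap of 0.5 SD with 67 per group, the corresponding figures are 18% (r = 0) and 5% (r = 0.6).

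**Hypothesis C: chance of a non-significant result if the paired test were run.** SE = sqrt(2(1 − r)/N).

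| N | r | SE | True loss 0.2 SD | True loss 0.25 SD |
|---|---|---|---|---|
| 134 | 0.5 | 0.086 | 37% | 18% |
| 134 | 0.7 | 0.067 | 16% | 4% |
| 192 | 0.5 | 0.072 | 21% | 7% |
| 192 | 0.7 | 0.056 | 6% | 1% |

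On the assumed 0.5 SD gain, these losses are 40% and 50% of the benefit. At r = 0.3 and N = 134 the two miss rates would be 51% and 32%.

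**Can the data support a margin-based claim?** Take 0.25 SD purely as an illustration.

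- C, non-inferiority at one-sided 0.025, N = 134, no true loss: power = Φ(0.25/SE − 1.96). At r = 0.5, Φ(0.93) is about 0.82; at r = 0.6, Φ(1.28) is about 0.90; at r = 0.7, Φ(1.78) is about 0.96. For 80% power the total needed is 126 at r = 0.5 and 176 at r = 0.3.
- B, two one-sided tests at 0.05, 67 per group, no true gap: power = 2Φ(0.25/SE − 1.645) − 1. At r = 0.6 this is 2Φ(0.164) − 1 = 0.13. For 80% power it would take 206 per group at r = 0.5 and 140 at r = 0.7.

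C can therefore be tested against a margin of that size if r is about 0.5 or more. B cannot.

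**The case against.** Only C states the inference from non-significance. B predicts a non-significant result without calling it equivalence, and it has its ANCOVA, which would ordinarily yield an adjusted difference with an interval. That stands: the missing analysis concerns C alone, and for B the point is the criterion.

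C also requires week 40 to be significantly below baseline. A reader might infer that small or noisy data make C easier to confirm. The text does not support this, because the first half becomes harder with such data. In a simulation of a 0.5 SD gain with half of it lost (r = 0.5), both halves held about 17% of the time at N = 20, 31% at N = 80, 17% at N = 134 and 7% at N = 192.

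A reader might likewise infer that the rule rewards attrition. Section 5.2 specifies intention-to-treat analysis with imputation, so dropout need not shrink the analysed number.

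Week 40 falls 32 weeks after treatment for Group 1 and 24 weeks for Group 2, and one might call that an error. It is not: section 4 counts the six months from the point at which both groups have finished, and the week numbers agree with that.

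Finally, a statistical analysis plan not shown here could add the missing contrast and a margin. It could, but the criterion itself is written into the protocol's hypotheses.

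**Conclusion.** The point holds for C in full. The maintenance claim rests on an invalid criterion, and the protocol's own list of analyses contains no test for it. It holds for B as to the criterion only: a remaining gap of 0.3 SD would go undeclared in 42% to 59% of trials with 67 per group, or 27% to 46% with 96 per group after imputation.

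It would go too far to say that both claims would often be made falsely. At N = 134, a loss of half the assumed gain would be missed only 4% to 18% of the time for r from 0.7 to 0.5, and a between-group gap of 0.5 SD would seldom be missed. The fault lies in the logic of the criterion. Its practical weight is greatest for gaps in B up to about 0.3 SD and for losses in C of up to about 0.2 SD.

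These sizes depend on the assumed correlations, two-sided testing, and d = 0.5 as the reading of a moderate effect. Hypothesis A, the primary test, is unaffected, so this should be corrected but does not threaten the main result.

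**What to change.** **Hypothesis C.** Add a within-person contrast of week 40 with each participant's own end-of-treatment score (week 8 for Group 1, week 16 for Group 2), with group as a factor. Claim maintenance only if the upper 95% confidence limit for worsening lies below a margin that the sponsor sets and justifies in advance. Keep the comparison with baseline as it is.

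**Hypothesis B.** Drop the absence of a significant difference as the criterion. Report the adjusted week-16 difference with its 95% confidence interval, and make no claim of equivalence, since the sample cannot support one at a margin near 0.25 SD.

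**Cost.** Rewording, plus one contrast on data already collected. The claims become harder to make, and a margin has to be chosen without a stated OLBI standard deviation. If the correlation between assessments is nearer 0.3 than 0.5, 134 participants would fall short of 80% power for C at a 0.25 SD margin.

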### 4. Study design

This will be a pragmatic, stepped wedge, open-label, randomised controlled trial. Consenting NHS staff will be randomly assigned to two groups, by a research assistant using a computerized randomization algorithm (applying a simple 1:1 randomization schedule). The study will be carried out in four phases, which are illustrated in Figure 1.

Figure 1. Stepped wedge trial design

Participants in both groups will be asked to complete outcome measures during a pre-intervention baseline assessment (week 0). After the baseline assessment, only participants in group 1 will access an 8-week intervention (controlled phase). Next, group 2 will access the intervention during an 8-week period (full implementation phase). Finally, we will collect further outcome measures 6 months after both groups have completed the intervention (follow-up phase). The outcome measures will be completed continuously at each of the measurement points outlined in the above timeline (weeks 0, 8, 16, 40). All measures will be completed online using an industry-standard survey system (Qualtrics – which automatically sends email reminders to consenting participants), which will be managed by a research assistant.

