#### 4.4. Recruitment, study procedures and data collection

##### *Participant recruitment process*

- The RDaSH NHS Trust research team will promote the study using usual channels of communication with staff: newsletter circulated via email from the NHS communications team, via the staff intranet front page, and via posters placed in communal areas (i.e. cafeterias, meeting rooms, hospital corridors). A standard promotional leaflet will be promoted through these methods (see Appendix).
- Potentially eligible participants will receive copies of the study information sheet in three ways: (1) via email from the research team; (2) printed copies distributed to the team base and placed in staff inboxes; (3) printed copies distributed by a clinical studies officer at local team meetings.
- Potential participants will have the opportunity to contact the research team to clarify questions, if necessary, prior to the deadline for providing consent to participate (within 2 weeks). They will be asked to provide consent electronically using an online consent form which will be accessible through a weblink embedded in the information sheet. This method will ensure that no paper copies can be lost or misplaced in the post, and will be an efficient way to gather informed consent using an industry-standard and secure survey system (Qualtrics). An sample text for the consent form that will be available electronically is provided in the Appendix. The promotional material will clearly indicate the deadline for application to participate. NHS managers and/or team leaders will not be involved in the consenting process, which will minimise administrative burden and the potential for selection biases or the application of undue pressure on potential participants.
- Consenting participants will be randomly allocated to the immediate intervention group (group 1), or the waitlist control (delayed intervention) group. Allocation will be carried out by the research team, using a computerized randomization schedule, and will be communicated directly to study participants via email within a week of the application to participate deadline.

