### 5.2. Primary analysis

Trial data will be summarised using a CONSORT diagram and all analyses will be based on *intention-to-treat* principles. Missing data will be imputed using an expectation-maximization algorithm, prior to conducting formal analyses.

The primary hypothesis test (A) will be based on comparing mean outcome measures between groups at week 8, as shown in Figure 1. Mean OLBI scores will be compared between groups using analysis of covariance (ANCOVA), controlling for baseline severity.

Sensitivity analyses will be performed to assess the robustness of the main findings. This will involve repeating the comparison of means whilst controlling for any potential site-effects (systematic differences in burnout between NHS services), introducing a site variable as a random effect.

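### Allocation is one batch draw by simple 1:1 randomisation with no restriction by service: valid, but stratifying by care group would remove avoidable chance imbalance at little cost

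*Protocol*

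**What the plan says.** - **Method of allocation.** Section 4 of the protocol has participants assigned "by a research assistant using a computerized randomization algorithm (applying a simple 1:1 randomization schedule"). It names no blocking, stratification or minimisation, and neither does any other section.
- **Timing.** Section 4.4 (Participant recruitment process) sets a deadline for consent. The allocation "will be communicated directly to study participants via email within a week of the application to participate deadline". Facilitators receive the participant list once randomisation is finished. In effect the whole sample is allocated in one batch.
- **Population.** Section 4.1 recruits from community services in all four care groups of the Trust, covering children and adults and a wide range of clinical work.
- **Analysis.** Section 5.2 makes the primary test an ANCOVA of week-8 OLBI adjusted for baseline severity. Service enters only in a sensitivity analysis, "controlling for any potential site-effects (systematic differences in burnout between NHS services), introducing a site variable as a random effect".
- **Sample size.** Section 5.1 assumes a moderate effect, and "we estimate that at least 67 participants are needed per group". That is 134 in total, raised to 192 for 30% dropout.
- **Source of the service variable.** Section 4.3 lists generic work-setting information among the items participants report. Section 4.4 (Data collection and safeguarding procedures) collects demographics and role information on paper forms without names, pseudonyms or identifiers, and section 6.1 describes data from section 4.3 as fully anonymous. Section 4.4 also plans an electronic survey two weeks after randomisation. It is called anonymised and then said to be held in pseudonymised files, and its listed examples do not include service or care group.

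**The concern.** Simple randomisation is most useful when people are enrolled one at a time and the next allocation must stay unpredictable. Here everyone has consented before the list is run, so restricting the draw gives nothing away. Without restriction, the mix of services in the two arms is left to chance in a single draw that cannot be repeated.

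The protocol itself regards differences between services as worth examining, but does so only after the primary result. It is also unclear whether the variable needed for that check will be linked to the OLBI scores. If site means the four care groups, a random effect with four levels would be poorly estimated as well.

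At stake is the precision and credibility of the week-8 comparison. The trial is open-label with a self-reported outcome, and a visible service imbalance would invite doubt that a weak sensitivity analysis could not settle.

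**Working it through.** **1. The plan's own figures.** 134 / (1 − 0.30) = 191.4, rounded up to 192. Per arm, 67 / 0.70 = 95.7, rounded up to 96. The protocol never states 96 per arm; it is implied by 192 / 2. The protocol gives no number for a moderate effect. Taking d = 0.5, two-sided alpha 0.05 and no credit for the baseline correlation, a noncentral t calculation gives 64 per group for 80% power. The stated 67 gives 81.9%.

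**2. Arm sizes under simple allocation of 192.** Arm size is Binomial(192, 0.5), with SD = √(192 × 0.25) = 6.9 and a central 95% range of 82 to 110. An exact 96/96 split has probability 5.75%. Power depends on the two arms jointly, through n₁n₂/(n₁ + n₂). After 30% loss:

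| Split | Expected completers | Power at d = 0.5 |
|---|---|---|
| 96/96 | 67.2 / 67.2 | 82.0% |
| 90/102 | 63.0 / 71.4 | 81.9% |
| 82/110 | 57.4 / 77.0 | 81.2% |
| 76/116 | 53.2 / 81.2 | 80.3% |

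The smaller arm is 76 or fewer in 0.5% of draws, so power is at or above 80% in more than 99% of draws. Averaged over the binomial split, power is 81.8%, against 82.0% for forced 96/96.

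**3. Service mix.** The protocol gives no care-group sizes, so these are assumptions.
- For a care group of 24, a split of 2:1 or worse means 8 or fewer in one arm: 2 × P(X ≤ 8), X ~ Binomial(24, 0.5), which is 2 × 0.0758 = 0.15.
- The same probability is 0.21 for a group of 16, 0.05 for 32 and 0.03 for 48. With groups of 96, 48, 32 and 16, at least one splits this badly in about 27% of draws, mostly because of the group of 16.
- With four equal groups of 48, the difference between arms in one group's share has SD = √(0.25 × 0.75 × 2/96) = 0.0625. A difference above 10 points is 0.10/0.0625 = 1.6 SDs, probability about 11% per care group.

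**4. What such an imbalance does to the estimate.** A group of 24 split 16:8 in arms of 96 makes up 16.7% of one arm and 8.3% of the other, a gap of 8.3 points. If that service differs from the rest by an assumed 0.5 SD, the raw shift is 0.083 × 0.5 = 0.04 SD before baseline adjustment. The assumed effect is 0.5 SD, and the standard error of the difference at 67 per arm is √(2/67) = 0.17 SD.

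**5. What adjusting for care group could gain.** If care group explains a share s of the residual variance, the effective d is 0.5/√(1 − s). At 67 per group, allowing for the extra degrees of freedom, power is 82.3% for s = 1%, 83.8% for s = 5% and 85.7% for s = 10%, against 81.9% without adjustment. The share is not known from the protocol.

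**The case against.** The strongest reply is that simple 1:1 randomisation is valid at this size and nothing here is stated wrongly. That stands. Services are balanced in expectation, chance imbalance is already reflected in the type I error, and the primary ANCOVA adjusts for each nurse's own baseline burnout, the main route by which service differences in level would enter. What is left is services whose burnout changes differently over the eight weeks, plus whatever service variance baseline OLBI does not capture. By step 4 a typical shift is small.

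A reader might infer more than the protocol supports, in four ways:

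- **That the 67 per group is put at risk.** One arm does fall below 96 in about 94% of draws, but the power cost is 0.2 points on average. Forcing 96/96 would not secure 67 in both arms either: with random dropout this happens in about 32% of trials, against 20% under simple allocation. The synopsis also calls 192 a minimum.
- **That the sponsor expects service differences.** Section 5.2 speaks only of potential ones and treats them as a precaution.
- **That uneven arms would upset delivery.** Section 4.4 tells facilitators the numbers after randomisation and lets staff attend any of four weekly slots. An 82/110 split is about 21 against 28 per slot, and no capacity limit is stated.
- **That the site analysis cannot be done.** The survey files are described as pseudonymised, so linkage is unclear rather than ruled out.

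**Conclusion.** The point holds as an optional, low-cost improvement. The allocation is unbiased and the stated sample size is not endangered. The weakness is that service mix is left to chance in an irreversible single draw although the full list is known beforehand, and that the only planned check on service rests on a variable whose link to the outcome data is doubtful.

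The gain from changing it is modest: it removes imbalances that are fairly common (about 15% for a 2:1 split in a group of 24) but shift the estimate by only a few hundredths of an SD. It also yields between a fraction of a point and about 4 points of power, depending on how much residual variance care group explains. These figures rest on d = 0.5, a two-sided test, equal dropout in the arms, and assumed care-group sizes, service differences and variance shares.

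**What to change.** 1. Add care group (or service, whichever is to count as site) to the online consent form, so that it is held under the participant's identifier.
2. In sections 4 and 4.4, replace simple randomisation with 1:1 permuted-block randomisation stratified by care group, run once on the closed list of consented nurses from a saved seed.
3. In section 5.2, include the stratum as a fixed effect in the week-8 ANCOVA. The random-effect sensitivity analysis can then be kept for a finer service variable if one is recorded.

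The cost is one extra consent-form item, a different setting in the randomisation program, a short change of text and a few degrees of freedom (three for four care groups). Predictability of block allocation is not a concern, because all consent is complete before the list is run. If stratification is not adopted, item 1 is still worth making, since it gives the planned site analysis a usable variable.
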